6.6 Contraception

Women of child-bearing potential, defined as all women physiologically capable of becoming pregnant, can be included in the study provided they are using highly effective methods of contraception during dosing and for 6 months after the last dose of IMCgp100.

Highly effective contraception methods include the following:

- Total abstinence from sexual relations for the duration of the treatment when applicable to the lifestyle of the patient. Periodic abstinence (e.g., calendar, ovulation, symptothermal, post-ovulation methods) and withdrawal are not acceptable methods of contraception
- Female sterilization (have had surgical bilateral oophorectomy with or without hysterectomy) or tubal ligation at least 6 weeks before taking study treatment. In case of oophorectomy alone, this applies only when the reproductive status of the woman has been confirmed by follow-up hormone level assessment
- Male sterilization (at least 6 months prior to Screening). For female patients on the study the vasectomized male partner should be the sole partner for that patient
- The combination of any 2 of the following methods when both are used simultaneously:
 - Use of oral, injected, or implanted hormonal methods of contraception or other forms of hormonal contraception that have comparable efficacy (failure rate < 1%), for example hormone vaginal ring or transdermal hormone contraception
 - Placement of an intrauterine device or intrauterine system

- Barrier methods of contraception: condom or occlusive cap (diaphragm or cervical/vault caps) when used with spermicidal foam, gel, film, cream, or used of a spermicidal vaginal suppository

6.7 Patient Numbering and Treatment Assignment

6.7.1 Patient Numbering

Each patient is identified in the study by a number that is assigned when the patient is first enrolled for Screening. The patient number is retained as the primary identifier for the patient throughout participation in the trial. The patient number consists of the center number assigned by the Sponsor and a sequential patient number suffix so that each patient is numbered uniquely across the entire database. Patient numbers will be assigned by the Sponsor via the interactive response technology system at the time of Screening.

6.7.2 Treatment Assignment and Randomization

Patients enrolled in the Phase 1 portion of the study will be assigned to the appropriate open Phase 1 cohort by the Sponsor. Patients enrolled in the expansion cohort will be assigned by the Sponsor. Assignments will be coordinated via the interactive voice response system for the study.

6.8 Study Drug Packaging/Labelling, Preparation and Dispensation

Further instructions for the preparation and dispensation of IMCgp100 are described in the study Pharmacy Manual, relevant Pharmacy Handling Instructions and [Section 6.1](#) Study Treatment.

Packaging and labelling details are outlined in the study Pharmacy Manual and relevant Pharmacy Handling Instructions.

All dosages prescribed to the patient and all dose changes during the study must be recorded on the Dosage Administration Record eCRF.

6.8.1 Study Drug Compliance and Accountability

Study treatment will be administered to the patient by the trained study site staff at the study sites and as outlined in the study Pharmacy Manual and [Section 6.1](#). Compliance with the prescribed regimen will be assured by administration of the study treatment under the supervision of investigator or his/her designee.

The investigator or designee must maintain an accurate record of the shipment and dispensing of study treatment according to local institutional drug accountability processes. Full drug accountability for IMCgp100 is required in accordance with the International Conference on Harmonisation (ICH) Good Clinical Practice guidelines. Drug accountability will be noted by the field monitor during site visits and at the completion of the study. At study close-out, and, as appropriate during the course of the study, the investigator will return all used and unused study treatment, packaging, drug labels, and a copy of the

completed drug accountability logs to the site study monitor. Additional details including receipt of study products, storage and management of temperature excursions are provided in the study Pharmacy Manual.

6.8.2 Drug Supply, Storage, and Disposal

Study treatments must be received by designated personnel at the study site, handled and stored safely and properly, and kept in a secured location to which only the investigator and designated site personnel have access. Upon receipt, IMCgp100 supply should be recorded and stored according to the instructions specified on the drug labels.

All IMCgp100 supply remaining at the end of the study, following appropriate drug accountability procedures at each site, can be destroyed per local institutional practice at the study site or at a third party vendor as appropriate and agreed to with Sponsor. All destruction of study medications must be documented appropriately.

6.9 Management and Follow-up of Toxicity

Patients whose treatment is interrupted or permanently discontinued due to an AE or clinically significant laboratory value, must be followed-up at least once a week (or more if clinically indicated) for 4 weeks, and subsequently at approximately 4-week intervals, until resolution or stabilization of the event, whichever comes first. Appropriate clinical experts should be consulted as deemed necessary for any AEs observed in the course of the trial. In the case of a toxicity suspected to be related to a cytokine release syndrome, the immunologic assessments outlined in [Section 7.3.7.7](#) should be performed. In case of a worsening rash or other related skin toxicity (e.g., pruritus), a skin punch biopsy, as outlined in [Section 7.3.7.10](#), should be considered.

Guidelines for management of AE and dose modifications are presented below in [Table 6-5](#) (below). Institutional protocols for management of immune-related AE should be implemented in cases of immune-related AE and will take precedence over guidance in [Table 6-5](#). All patients must be followed up for the occurrence of AE and SAE for 90 days following the last dose of IMCgp100. If more than 3 consecutive doses of single-agent IMCgp100 are not administered due to drug-related toxicities or if a treatment gap occurs of greater than 21 days, the default position is that then the patient must be discontinued from the study. However, if a patient who misses more than 2 consecutive doses due to a drug-related toxicity is experiencing clinical benefit, and in the opinion of the investigator it is in the patient's best interest to remain on study, then the patient may restart treatment after discussion with the Sponsor.

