The **Disease Progression Follow-up Period** is defined for all patients who discontinue for reasons other than death, progressive disease (PD) per Response Evaluation Criteria in Solid Tumors version 1.1 (RECIST v.1.1) or modified irRECIST as outlined below, lost to follow up, withdrawal of consent, or study termination.

- All patients who discontinue for reasons other than PD per RECIST v1.1 will be followed with imaging until evidence of PD per RECIST v.1.1 (see [Section 7.2.4](#) and [Section 7.3.1](#))
- For patients who consent to and continue treatment beyond progression per RECISTv.1.1, imaging should continue until progression per modified irRECIST (irPD) or treatment discontinuation.
- If patients choose not to return for these visits or are unable to do so, every effort should be made to contact them or a knowledgeable informant by telephone to determine if the patient has had disease progression. .
- Patients who discontinue treatment for reasons of disease progression by either RECISTv1.1 or modified irRECIST criteria will not enter the Disease Progression Follow-up Period.
- Anti-neoplastic therapies since discontinuation of study drug will be collected during this follow-up period.

The **Survival Follow-up Period** will initiate after either the 90-day Follow-up Period (in patients who have discontinued for PD) or after the Disease Progression Follow-up Period (for patients discontinuing study treatment for reasons other than PD) and continue until death. As possible, all patients will be followed for survival until the end of the study is reached. Anti-neoplastic therapies since discontinuation of study drug will be collected during this follow-up period.

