3.4 End of Treatment

In all patients in this study, IMCgp100 will be administered IV according to the defined regimen. Reasons for discontinuation of study treatment are described in [Section 6.10](#).

Patients who discontinue treatment will remain in the study and be followed for the overall survival (OS) endpoint.

Each patient's disease will be assessed for efficacy using 2 sets of criteria: (1) RECIST v.1.1 and (2) modified irRECIST. The objective response rate (ORR) endpoint will be assessed as ORR per RECIST v.1.1; however, patients experiencing PD per RECIST v.1.1 criteria may consent to continue to be treated until meeting the criteria for unequivocal, confirmed PD by modified irRECIST as defined in [Section 13.2.1](#).

Please refer to [Section 6.9](#) for details regarding imaging assessment of PD for purposes of treatment discontinuation.

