6.10 Treatment Discontinuation

Reasons for discontinuation of study treatment will include:

- Unequivocal, confirmed disease progression referring to the modified irRECIST criteria ([Wolchok, 2009](#); [Nishino, 2013](#); [Bohnsack, 2014](#); refer to [Section 6.10.1](#) and [Appendix 1](#))
- Initiation of alternative anti-cancer therapy including another investigational agent
- Unacceptable toxicity defined as an AE that, in the opinion of the investigator or the Sponsor, contraindicates further dosing
- Withdrawal of consent from further treatment with investigational product by the patient or the investigator or lost to follow-up
- Patient is determined to have met 1 or more of the exclusion criteria or failed to meet all of the inclusion criteria for study participation AND continuing to receive investigational product might constitute a safety risk. Patients who fall into this category and for whom continuation of treatment is not thought to pose a safety risk in the opinion of the investigator may continue to receive study treatment after discussion with the Sponsor Medical Monitor
- Pregnancy or intent to become pregnant

At the time patients discontinue study treatment, the EOT visit should be scheduled as soon as possible and in the appropriate window of 14 days after the last dose was administered. At this visit, all of the assessments listed for the EOT visit will be performed (see [Table 7-1](#)). If the decision to withdraw the patient occurs at a regularly scheduled visit, that visit may become the EOT visit rather than having the patient return for an additional visit (safety follow-up will still continue for the full 90-day observation period, see [Section 7.2](#) for details of assessments required at EOT). An End of Treatment Phase Disposition eCRF page should be completed at the EOT visit, giving the date and reason for stopping the study treatment. End of treatment/premature withdrawal visit is not considered as the end of the study. Patients should still be followed for survival information and, if the patient does not have PD, imaging data should continue to be collected to capture progression based on RECISTv.1.1.

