Patients who discontinue study treatment should NOT be considered withdrawn from the study as they will be followed for the OS endpoint. They should return for the assessments indicated in [Section 7](#) and [Table 7-1](#). If they fail to return for these assessments for unknown reasons, every effort (e.g., telephone, email, and registered letter) should be made to contact them. If a patient discontinues study treatment, but continues study assessments, the patient remains on study until such time as he/she completes protocol criteria for ending study assessments. At that time, the reason for study completion should be recorded on the Study Disposition eCRF page.

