7.2.2 Discontinuation of Study Treatment and End of Treatment Visit

Patients may voluntarily discontinue from the study treatment for any reason at any time. If a patient decides to discontinue from the study treatment, the investigator should make every effort to determine the primary reason for this decision and record this information in the patient's chart and on the appropriate eCRF pages. Other reasons for discontinuation of study treatment are outlined in [Section 6.10](#).

Patients will be considered withdrawn from therapy if they state an intention to withdraw, and fail to return for visits or become lost to follow-up for any other reason.

The investigator should discontinue study treatment for a given patient if, on balance, he/she believes that continuation would be detrimental to the patient's well-being.

At the time patients discontinue study treatment, a visit should be scheduled as soon as possible, and within 14 days of the last dose of study drug or within 14 days of the decision to permanently discontinue study treatment, at which time all of the assessments listed for the EOT visit will be performed ([Table 7-1](#)). If the decision to withdraw the patient occurs at a regularly scheduled visit, that visit may become the EOT visit rather than having the patient return for an additional visit. An End of Treatment Phase Disposition eCRF page should be completed, giving the date and reason for stopping the study treatment. End of treatment/premature withdrawal visit is not considered as the end of the study.

Patients who discontinue study treatment should NOT be considered withdrawn from the study. They should return for the assessments indicated in [Section 7](#) and [Table 7-1](#). If they fail to return for these assessments for unknown reasons, every effort (e.g., telephone, email, postal letter) should be made to contact them. If a patient discontinues study treatment, but continues study assessments, the patient remains on study until such time as he/she completes protocol criteria for ending study

assessments. At that time, the reason for study completion should be recorded on the Study Disposition eCRF page.

7.2.3 90-day Safety Follow-up Period

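### Section 6.9 takes a patient with a long dosing gap out of the study, contradicting the sections that keep patients who stop treatment in imaging and survival follow-up

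*Protocol*

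**What the plan says.** Section 6.9 has two triggers: over three doses in a row missed because of drug-related toxicity, or a gap of more than 21 days, for which no cause is specified. The consequence is that "the default position is that then the patient must be discontinued from the study". An exception follows: a patient with clinical benefit whose missed doses were due to drug-related toxicity may restart after discussion with the sponsor. The same section keeps adverse-event follow-up for 90 days after the last dose. It says nothing about imaging or survival follow-up.

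The sections that govern follow-up read differently:

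- Section 3.4: "Patients who discontinue treatment will remain in the study and be followed for the overall survival (OS) endpoint".
- Section 3.3, repeated in substance in 7.2.4: "All patients who discontinue for reasons other than PD per RECIST v1.1 will be followed with imaging until evidence of PD per RECIST v.1.1".
- Section 6.10: "if the patient does not have PD, imaging data should continue to be collected to capture progression based on RECISTv.1.1", and "Patients who discontinue study treatment should NOT be considered withdrawn from the study as they will be followed for the OS endpoint".
- Section 7.2.2: "Patients who discontinue study treatment should NOT be considered withdrawn from the study".
- Section 7.2.5: survival contact every 12 weeks until death or the end of the study, unless the patient withdraws consent or is lost to follow-up.
- Section 6.11: the reasons given for leaving the study are death, loss to follow-up, withdrawal of consent to all further participation, and end of study.

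**The concern.** A mandatory instruction in the toxicity section removes from the study a group of patients whom the follow-up sections retain. PFS, DOR and OS are secondary endpoints. Section 9.6.1 analyses PFS and OS by Kaplan-Meier, and Section 9.10.2 wants the expansion data to show whether OS may exceed that of available therapies. If a site acts on 6.9 as written, a patient without progression leaves imaging and survival follow-up once a dosing gap becomes long enough. Where the gap is due to toxicity, the censoring time may be related to prognosis, and Kaplan-Meier estimates assume that it is not.

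**Working it through.** No arithmetic applies and the protocol has no figure to reproduce. The check sets the rules side by side and asks whether they can all hold.

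**1. Same patient, two instructions.** Take a patient with no RECIST v1.1 progression who has been off drug for more than 21 days and does not restart.

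| Question | Section 6.9 | Other sections |
|---|---|---|
| Still in the study? | No, by default | Yes (3.4, 6.10, 7.2.2) |
| Imaging to progression? | Not mentioned | Yes (3.3, 6.10, 7.2.4) |
| Survival contact? | Not mentioned | Yes (3.4, 6.10, 7.2.5) |
| Adverse-event follow-up? | Yes, 90 days | Yes, 90 days (7.2.3) |

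The first row is a direct contradiction.

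**2. Does the protocol distinguish study from study treatment?** Yes. Section 6.10 covers leaving treatment and 6.11 covers leaving the study. The two exits are also recorded separately. For the first, "An End of Treatment Phase Disposition eCRF page should be completed at the EOT visit". For the second, when study assessments end, "the reason for study completion should be recorded on the Study Disposition eCRF page". A site that follows 6.9 to the letter would complete the second page too early.

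**3. Could 6.9 be a deliberate exception?** Nothing supports that. Section 6.11 does not list a dosing gap, and 3.3 and 7.2.4 cover all patients who stop for reasons other than progression. Within 6.9, the exception sentence speaks of remaining on study when it means restarting treatment, and Table 6-5 takes patients with recurrent infusion reactions off study treatment, not off the study. Study treatment is very probably what was meant.

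**4. Where would a site look?** The dosing-gap rule stands only in 6.9. The list of reasons for stopping treatment in 6.10 does not name it, and the 6.9 paragraph does not refer to 6.10 or 7.2 for what happens next.

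**5. What would be lost per affected patient.** Imaging every 8 weeks to week 40 and every 12 weeks thereafter until RECIST v1.1 progression (7.2.4), and survival contact every 12 weeks (7.2.5).

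**6. By endpoint.**

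- PFS and DOR: censored at the last scan before exit.
- OS: contact ends. The death-registry checks allowed in 7.2.5 would recover some deaths, as far as local law permits.
- ORR, the primary endpoint: Section 7.3.1 requires an end-of-treatment scan if none was done in the previous 30 days, and that scan can confirm a response first seen at least 4 weeks earlier. A response first seen after treatment stopped counts under 9.6.1 if neither progression nor further anti-cancer therapy came first; it would be missed. The protocol gives no rate for this.

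**7. Which exits are related to toxicity?** The first trigger is, by definition. The 21-day trigger carries no cause, so it also catches gaps for other reasons.

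**The case against.** The strongest reply is that the document largely corrects itself. Section 6.11 omits dosing gaps, 6.10 and 7.2.2 put the NOT in capitals, and 3.3 and 7.2.4 apply to all non-progression stops. Section 6.9 itself requires continued adverse-event follow-up, which sits badly with a patient who has truly left. The protocol is also loose with the term elsewhere: the synopsis and 7.3.1 call stopping for progression study discontinuation, although those patients go on to survival follow-up. Harm therefore needs a site to follow one phrase against several explicit instructions, and no analysis set, denominator or endpoint definition changes.

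Most of this stands, and it limits the weight of the point. It does not remove the contradiction: 6.9 is current operative text, says must, and is the only place where the dosing-gap rule appears. The list in 6.11 is introduced by a word that leaves it formally open, so it does not settle the matter alone.

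The clinical-benefit exception is sometimes a tempting answer, but it does not close the gap. It permits a restart after toxicity-related misses. It does not restore follow-up for a patient who does not restart, and it is not worded for gaps with other causes.

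In the other direction, a reader might infer that the protocol plans to cut off follow-up in patients with toxicity, or that every such exit is informative censoring. Neither is supported. The follow-up sections keep these patients in, and the 21-day trigger does not depend on toxicity.

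**Conclusion.** The contradiction is real and certain as a matter of wording. It is very probably a drafting slip, not a planned truncation. The risk is confined to sites that apply 6.9 literally; there, PFS, DOR and OS follow-up would end early, with potentially informative censoring where toxicity caused the gap. Registry checks soften the effect on OS, and the end-of-treatment scan softens the effect on ORR. The size cannot be quantified, because the protocol gives neither the number of patients with such gaps nor any indication of how sites would read the rule, and no figure is assumed here. The phrase should be corrected because the correction is trivial and a mandatory rule should not depend on each site inferring the intended word.

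**What to change.** In Section 6.9, replace *discontinued from the study* with *discontinued from study treatment; imaging and survival follow-up continue per Sections 6.10, 7.2.4 and 7.2.5*. This is a wording change to the protocol only. It needs no extra patients, visits or scans, because the follow-up it refers to is already required.

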6.9.1 Hypotension

Cases of severe hypotension have been observed across the IMCgp100 clinical trials. Initial therapy for low-grade hypotension is aggressive IV fluid (crystalloid or colloid) therapy. In cases of hypotension, where blood pressures are not immediately responding to fluid management, IV corticosteroid therapy should be considered. Cases of hypotension not complicated by additional symptoms associated with cytokine

release syndrome (CRS) (e.g., nausea, vomiting, malaise, and fever) have been observed with IMCgp100. Retrospective analyses of peripheral cytokines in the IMCgp100-102 study have suggested that mild-to-moderate elevations in IL-6 after the first dose of IMCgp100 may be associated with more severe presentations of hypotension. Intervention with early IV corticosteroid in cases of hypotension without initial response to fluid therapy is warranted as described in [Table 6-5](#).

6.9.2 Cytokine Release Syndrome

Cases of CRS have been observed across the IMCgp100 clinical trials (as of 12 August 2018, CRS cases have been seen in 6% of patients in the current study overall, and 2 of these cases were \geq Grade 3). The pattern of CRS generally begins 2–12 hours following the first 3 doses of IMCgp100 and the observed toxicities include hypotension (which has been severe in some patients), rash or general erythema, pruritus, facial and general edema, pyrexia and chills. Other commonly reported symptoms, typically mild to moderate, include headache, fatigue, nausea, and vomiting. Grading of CRS is based on the modified grading system ([Table 6-5](#)). Aggressive management in cases of suspected CRS is warranted per guidance in [Table 6-5](#). Early intervention with immunosuppression therapy (e.g., high-dose corticosteroid therapy) is warranted in cases of suspected CRS.

Table 6-4 describes updated grading for events of CRS.

Table 6-4 Cytokine Release Syndrome Grading Scalea

Grade	Symptoms
1	Symptoms are not life-threatening and require symptomatic treatment only (e.g., fever, nausea, fatigue, headache, myalgia, and malaise)
2	Symptoms require and respond to moderate intervention: 
 • Oxygen requirement < 40% • Hypotension responsive to fluids or 1 low-dose vasopressor • Grade 2 organ toxicity
3	Symptoms require and respond to aggressive intervention 
 • Oxygen requirement > 40% • Hypotension requiring high-dose or multiple vasopressors • Grade 3 organ toxicity • Grade 4 transaminitis
4	Life-threatening symptoms 
 • Requirement for ventilator support • Grade 4 organ toxicity (excluding transaminitis)
5	Death

a. Lee 2014.

Table 6-5 Recommended Management and Dose Modifications of IMCgp100 by Toxicity Grade for Study Medications

Worst Toxicity NCI CTCAE v4.03 Grade	Recommended Management and Dose Modifications
Skin Toxicity	
Pruritus	
Grade 1	Continue dosing. If symptomatic, consider systemic antihistamine regimen (see grade 2 guidance below).
Grade 2	
Treat according to institutional practice and/or implement guidance below. Use systemic management and/or local skin management as indicated by symptoms.
 
Anti-pruritic regimen:
 
 1. Systemic antihistamine regimen recommended as first-line management of pruritus. Non-sedating, long-acting antihistamine (cetirizine, 10 mg oral or equivalent). If a sedating antihistamine is preferred (e.g., evening dosing) consider diphenhydramine 25 mg oral or intravenous. The use of sedating anti-histamines should be minimized in patients with co-morbid pulmonary pathology including pulmonary metastases or underlying inflammatory airways disease such as chronic obstructive pulmonary disease or asthma 2. Topical corticosteroid regimens Preparation of recommended regimens: 
 • For face and/or intertriginous areas (including genitalia) recommend alclometasone 0.05% or hydrocortisone 2.5% creams • For other body areas (i.e., trunk and extremities), recommend clobetasol or betamethasone 0.05% creams. Consider spray preparation for ease of application on trunk. For scalp involvement, consider a foam preparation 
Prophylaxis for subsequent doses is generally not required after grade 2 pruritus, but a non-sedating anti-histamine may be considered.

Grade 3	
Hold all doses of IMCgp100 until returned to NCI CTCAE grade ≤ 1.
 
Manage pruritus according to institutional protocol and guidance below.
 
Management: Treat according to institutional practice which generally includes an anti-pruritic regimen (see grade 2 management above). In addition, corticosteroid treatment (oral or intravenous) can be considered for pruritus that does not respond to antihistamine therapy (recommend oral prednisone 20–40 mg or a single dose of 25 mg hydrocortisone intravenous or the equivalent for refractory pruritus). For recommended systemic or topical regimens, refer to grade 2 management above).
 
Prophylaxis: In patients experiencing grade 3 pruritus, administration of a non-sedating antihistamine prophylaxis dose is recommended for the subsequent dose of IMCgp100, approximately 1–2 hours prior to the IMCgp100 dose being administered (e.g., cetirizine 10 mg or equivalent).
 
Prophylaxis with corticosteroid can be considered if pruritus recurs at a similar or worse severity despite antihistamine prophylaxis (recommend oral

Worst Toxicity NCI CTCAE v4.03 Grade	Recommended Management and Dose Modifications
	prednisone 20–40 mg or a single dose of 25 mg hydrocortisone intravenous or the equivalent). If steroid prophylaxis is used, the steroid dose should be titrated to the minimum effective dose and ultimately discontinued if possible.
Rash/Photosensitivity	
Grade 1	Continue dosing. If symptomatic, consider systemic antihistamine regimen according to management guidance for pruritus (above).
Grade 2	
Hold all doses of study IMCgp100 until returned to NCI CTCAE grade ≤ 1.
 
Use local skin management and systemic antihistamine regimen as indicated for symptoms. With observation of bullous formation or blistering rashes, consider dermatology consultation to rule out other causes (e.g., bullous pemphigoid). Oral or topical corticosteroids can be used for bullous formations or blistering. If bullous formation or blistering recur, consult Sponsor Medical Monitor for guidance.
 
Antihistamine (anti-pruritic) regimen:
 
 Systemic antihistamine regimen recommended as first line management of pruritus. 
 Non-sedating, long acting antihistamine (cetirizine, 10 mg oral or equivalent). If a sedating antihistamine is preferred (e.g., evening dosing) consider diphenhydramine 25 mg oral or intravenous. The use of sedating anti-histamines should be minimized in patients with co-morbid pulmonary pathology including pulmonary metastases or underlying inflammatory airway disease such as chronic obstructive pulmonary disease or asthma Use of oral corticosteroid dosing for shorter time frames (e.g., 3 days or fewer) may not require tapering dosing Topical corticosteroid regimens 
Preparation of recommended regimens:
 
 For face and/or intertriginous areas (including genitalia) recommend alclometasone 0.05% or hydrocortisone 2.5% creams For other body areas (i.e., trunk and extremities), recommend clobetasol or betamethasone 0.05% creams. Consider spray preparation for ease of application on trunk. For scalp involvement, consider a foam preparation
Grade 3	
Hold all doses of IMCgp100 until returned to NCI CTCAE grade ≤ 1.
 
Management:
 
Treat according to institutional practice which generally includes an anti-pruritic regimen (see grade 2 management above). In addition, corticosteroid treatment (oral or topical) can be considered for symptomatic rash that does not respond to anti-pruritic regimen. For topical regimens, refer to grade 2 management above.
 
Oral or topical corticosteroids can be used for bullous formations or blistering. If bullous formation or blistering recur, consult Sponsor Medical Monitor for guidance.

	
Dose adjustments:
 
If grade 3 rash observed with IMCgp100 resolves to NCI CTCAE grade ≤ 1 within 7 days, restart at the same dose level. If grade 3 rash resolves to NCI CTCAE grade ≤ 1 in 7–21 days, restart with 1 dose-level reduction in IMCgp100¹.

Grade 4	
Any grade 4 rash regardless of presentation, permanently discontinue IMCgp100. Manage according to institutional practice, consultation with a dermatologist is recommended.

Hypotension	
Mild, asymptomatic decrease ² : e.g., < 15 mmHg systolic blood pressure Grade 1	
Increase frequency of vital sign assessments to every 2 hours.
 
Consider maintenance intravenous fluids if mild decrease in blood pressure (e.g., systolic blood pressure < 110 mmHg or decrease in SBP of approximately less than 15 mmHg).
 
 Admit for inpatient monitoring (unless already hospitalized per protocol). Consider associated symptoms present and consider diagnosis of cytokine release syndrome (see below) Administer bolus intravenous fluids at a rate of approximately 1 L crystalloid per hour. If hypotension does not resolve with intravenous fluid therapy, consider intravenous corticosteroid therapy (e.g., methylprednisolone 2 mg/kg initial dose or equivalent) 
Consider prophylactic electrolyte supplementation for patients receiving intravenous fluids with low-normal serum phosphorus or magnesium electrolyte levels.

Moderate, asymptomatic decrease ² : e.g., ≥ 15 mmHg, but < 35 mmHg systolic blood pressure Grade 2	
Increase frequency of vitals to every 1 to 2 hours, or more frequently as medically necessary.
 
Monitor fluid balance status with careful attention to clinical volume status, as assessed by degree of peripheral edema or rales on pulmonary examination.
 
Administer bolus intravenous fluids at a rate of approximately 1 L crystalloid per hour. If the patient is asymptomatic and non-orthostatic after infusion of 2–3 L administered over 2–3 hours, consider transition to maintenance intravenous fluids until resolved.
 
If hypotension is not rapidly resolved with intravenous crystalloid therapy, add intravenous corticosteroid therapy of methylprednisolone 2 mg/kg initial dose or equivalent
 
Consider prophylactic electrolyte supplementation for patients receiving intravenous fluids with low-normal serum electrolyte levels.

Moderate, symptomatic decrease ² : e.g., ≥ 15 mmHg and orthostasis Grade 3	
Increase frequency of vitals to every 1 hour, or more frequently as medically necessary.
 
Administer bolus intravenous fluids at a rate of approximately 1 L crystalloid per hour. If the patient has symptomatic orthostatic hypotension after infusion of 2–3 L administered over 2–3 hours, consider administration of corticosteroids such as intravenous methylprednisolone 2 mg/kg or equivalent.
 
Initiate vasopressor therapy as required to maintain blood pressure.

	
Consider prophylactic electrolyte supplementation for patients receiving intravenous fluids with low-normal serum electrolyte levels.
 
If appropriate, consider additional measures according to the institutional cytokine release protocol (also see management of Infusion-related Reactions below).
 
If resolved within 48 hours of onset, no change in dosing is necessary. If repeat hypotension occurs, consult with the Sponsor Medical Monitor prior to subsequent dosing. Please refer to guidance for continued inpatient monitoring to determine need for continued inpatient monitoring (Section 6.2).
 
Consider the diagnosis of cytokine release syndrome and management (below).


Severe, symptomatic decrease²: e.g., ≥ 35 mmHg systolic and symptomatic when supine or mean arterial pressure³ ≤ 55 mmHg
 
Grade 4
	
Immediately administer high-dose intravenous corticosteroid therapy of methylprednisolone 2 mg/kg initial dose or equivalent. Maximize vasopressor therapy and fluid management. Administer bolus intravenous fluids (1 L crystalloid as rapidly as feasible) and consider escalation to higher level of care i.e., intensive care unit).
 
Consider maximal immunosuppression with high-dose intravenous corticosteroid therapy and consider additional measures (e.g., anti-IL6, tocilizumab) as required.
 
If appropriate, aggressive fluid therapy as indicated and described above; consider additional measures according to prophylactic electrolyte supplementation for patients receiving intravenous fluids with low-normal serum electrolyte levels.
 
Monitor vital signs every hour until resolved.
 
Consider additional measures according to the institutional cytokine release protocol (also see management of Infusion-related Reactions / Cytokine Release Syndrome below).
 
IMCgp100 must be dose reduced or discontinued. The Sponsor Medical Monitor should be consulted for discussion of individual case management.

Infusion-related Reactions/Anaphylaxis (occurring during infusion)	

Grade 1
	
Administer medications for symptomatic relief as needed. Infusion interruption may be considered until resolution of the event (up to 4 hours). The infusion rate of the study medication may be decreased by 50%. If resolved with decreased rate of infusion, any subsequent infusions can be administered at the reduced rate.

Grade 2
	
Stop infusion and keep intravenous line open. Treat according to institutional practice. Provide all supportive measures as indicated. Provide supplemental oxygen and fluids, as needed.
 
Monitor vital signs (e.g., blood pressure, pulse, and temperature) until resolution. Administer medications for symptomatic relief as needed. Antihistamines, acetaminophen (paracetamol), or corticosteroids may be administered, as needed at the discretion of the investigator.

	
Restart infusion only once infusion reaction resolves (within 4 hours of initial start of infusion), ensuring there is minimum observation period of one hour from stop of initial infusion to restart at reduced rate. Administer oral pre-medication (e.g., 1000 mg of acetaminophen or paracetamol, 50–100 mg diphenhydramine hydrochloride or alternative antihistamine), 60 minutes prior to restarting the infusion, accounting for prior doses/time given for management of initial reaction. Restart infusion at 50% of previous rate under continuous observation. If the adverse event recurs at the reinitiated slow rate of infusion, and despite oral pre-medication, then permanently discontinue the patient from study treatment.

Grade 3 or 4	
Discontinue infusion immediately, and permanently discontinue patient from study treatment. Grade 3 infusion-related reactions that improve by at least 1 grade within 6 hours of onset with medical management will not require permanent discontinuation. If treatment is continued all guidance provided for the management of grade 2 reactions must be followed.
 
Manage severe infusion-related reactions per institutional standards. Provide supplemental oxygen, fluids, and other resuscitative measures as needed. Monitor vital signs (e.g., blood pressure, pulse, respiration, and temperature) until resolution.

Infusion-related Reactions/Cytokine Release Syndrome — refer to modified grading system provided in Table 6-4
	
Grade 1	
Symptoms are not life-threatening and require symptomatic treatment only (e.g., fever, nausea, fatigue, headache, myalgia, and malaise)
 
 Admit for inpatient monitoring (unless already hospitalized per protocols) and manage according to individual symptoms. Assess for potential infection and treat fever and neutropenia. Initiate bolus and/or maintenance intravenous fluids and carefully monitor fluid balance Consider prophylactic electrolyte supplementation for patients receiving intravenous fluids with low-normal serum electrolyte levels Vigilantly monitor for escalation to grade 2 cytokine release syndrome with frequent vital signs (e.g., every-hour vital signs). Strongly consider early, high-dose corticosteroid therapy with changes in vital signs (see grade 2 below)
